2. METHODOLOGY

2.1. Design: Randomized controlled trial of parallel groups.

2.2. Participants:

Sample size and statistical power:

The calculation of the sample size has been made from Objective 1, which focuses on detecting a clinically significant difference in BMI that is the primary outcome measure. Based on previous work that explored weight change in follow-ups after the application of neurocognitive training in people with overweight and obesity (Bazzaz et al., 2017, Kakuschke et al., 2018, Sze et al., 2015), we have selected the smaller sample size (Cohen's $d = 0.46$). With this data, considering the statistical method (models of repeated measures inter and intra subjects), the number of groups ($g = 3$), and assuming an alpha level of 0.05 and a power of 0.80, the resulting sample size calculated with G-Power was 105 participants. To date, no study has conducted a program based on the combination of different neurocognitive tasks that have been proposed as effective for the treatment of obesity, with a 6-month follow-up period. Thus, we opted for a conservative estimate increasing the number of participants to 150. Then, the study could suffer a sample loss of 30% from the initial session to the follow-up at 6 months and the statistical power would be still guaranteed. Previous studies that explored neurocognitive training to lose weight with different follow-up periods have showed smaller attrition rates [i.e., 16% in a 3-month follow up (Carbine et al., 2021); 12.3% in a 2-month follow-up (Forman et al., 2019); 3.4% in a 6-month follow-up (Lawrence et al., 2015)].

Participants:

The participants ($N=150$) will be randomly allocated to three groups: experimental group (neurocognitive intervention; $n=50$), active control group (sham intervention; $n=50$), and control group (treatment as usual; $n=50$).

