People between 18 and 55 years old will be candidates to participate in the study, with a good command of the Spanish language, a range of BMI between 25 and 39.9 kg/m², and with at least two electronic devices available (one tablet, computer or smartphone to attend the online meeting and one smartphone with a gyroscope to do the training with the apps). All candidates will be screened for medical and psychological disorders and excluded if they have: (i) traumatic, digestive, metabolic or systemic disorders that affect the central nervous system, autonomic or endocrine, (ii) cardiovascular or any other disorders that prevent physical exercise; (iii) psychopathological disorders or presence of severe symptoms in the Depression Anxiety and Stress Scale-21 (DASS-21); (iv) eating disorders or presence of criteria in the Questionnaire on Eating and Weight Patterns-5 (QEWP-5); (v) pharmacological or any other kind of treatment for losing weight at present; (vi) candidates for bariatric surgery; (vii) food conditions that could interfere with the stimulus of the program (allergies, sprue, vegetarianism, veganism); (viii) current pregnancy or breastfeeding (or expected pregnancy in the following six months); (ix) weight loss $>5\%$ on the 3 months previous to the program; (x) use of medication that affects weight; (xi) frequent use of alcohol or other drugs that affects food intake.

Sampling context:

The recruitment will be carried out through social media and the web of the project.

Randomization and blinding:

A randomization (minimization) through the software Minimizer® will be performed to avoid imbalances between the groups in age, sex, and BMI (Stout et al., 1994). The psychologists that conduct the assessments (screening, evaluation sessions and follow-ups) will be blinded to the group allocation during the whole project. Moreover, since all assessments will be computerized and online, they are not subject to the biases of the evaluator. Further, all participants will be blind to their condition. Also, the people who perform the statistical analyses will be blind to the condition of the groups, through the coding of the interventions. Only the therapist performing the interventions will not be blind to the allocation of the participants.

2.3. Interventions:

Pre-treatment interventions (all groups).

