2.4. Outcome measures:

Note: The measures have been selected attending to ADOPT (Accumulating Data to Optimally Predict Obesity Treatment), to generate evidence about the efficacy for obesity interventions (MacLean et al., 2018). These measures are marked with an asterisk (*).

(1) Main outcome measure

- a. BMI*: Height and weight will be measured to determine BMI. The weight and height for the calculation of the BMI (kg/m²) will be obtained with a pharmacy digital scale

BMI will check for the results of the whole program (the 4 intervention sessions), and will be registered weekly from session 1 to post-treatment assessment, and will be also registered at follow-ups (3- and 6-months post-treatment). In addition, the week before the pre-treatment assessment session, it will be recorded daily to obtain the baseline weight and then averaged.

(2) Secondary outcomes (changes in cognitive measures, changes in eating and physical exercise behaviors and body measures).

(2.1) Changes in cognitive measures.

- a. Approach-avoidance bias: The approach-avoidance bias will be calculated before and after the 1-week training with the Tilt Task app. Participants should zoom in or out the appetizing and healthy food images that appear on the screen, depending on the presentation format of the image (horizontal or vertical). Approach and avoidance trials will be 50% for each type of image (healthy vs. unhealthy). The average reaction time of the approach (pull) and avoidance (push) trials will be subtracted separately for healthy and unhealthy foods, with the positive and

negative scores representing approximation and avoidance bias, respectively (see Kakuschke et al., 2018 for a full description).

- b. Food inhibition assessment: Using the Food Trainer task, reaction time for the high-calorie and low-calorie foods paired 50% with the go and 50% with the no-go signal will be measured before and after the 1-week training with the app. The average response time for go and no-go items will be calculated according to the type of images (appetizing and healthy foods), and commission errors will be recorded (see Lawrence et al., 2015).

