- e. International Questionnaire about physical activity (IPAQ; www.ipaq.ki.se): Score on this questionnaire with 7 questions about physical activity during the last week, as well as time walking and sitting down.
- f. Number of daily steps (pedometer): A pedometer will be used to register daily number of steps through the whole program.

(2.2.3) Adherence to healthy eating and exercise

- g. Healthy eating with a Visual Analog Scale, with the question: During the last week, how healthy do you think your diet has been? Healthy eating is understood

as that according to the information received in the program: low amount of ultra-processed food, added sugar or alcohol; high amount of whole grain products, fruits and vegetables; etc. (0= no healthy at all; 100= 100% healthy).

h. Exercise habits with a Visual Analog Scale, with the question: During the last week, what has been your level of activity and physical exercise? (0= no activity at all; 100= maximum level of activity that I would be able to do).

(2.3) Changes in body measures (body fat distribution):

a. **Waist circumference* (WC):** Participants should stand with heels close together and trunk erect, and put the tape measure around the waist, just above the navel, to measure the waist circumference in centimeters.

b. **Waist-to-hip ratio* (WHR):** Participants should stand with heels close together and trunk erect. To measure waist circumference, participants should put the tape measure around the waist, just above the navel. To measure hip circumference, participants should place the tape measure at the maximum gluteal prominence. The hip-to-waist ratio is determined by dividing the waist circumference (in cm) by the hip circumference (in cm).

c. **Waist-to-height ratio (WHtR):** Participants should stand with heels close together and trunk erect, and put the tape measure around the waist, just above the navel, to measure the waist circumference in centimeters. The height in centimeters will be measured with a digital weight. The waist to hip ratio is determined by dividing the waist circumference by the height.

(3) Mediating/moderating variables:

(3.1) Affect, stress and nonhomeostatic eating:

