3. PROCEDURE

All assessments and intervention sessions will be delivered online. Inclusion and exclusion criteria will be checked through the data collected in a questionnaire of sociodemographic and clinical variables. Further, psychopathology exclusion criteria will be tested with two questionnaires to measure depression, anxiety, and stress symptoms as

well as binge eating and bulimia (DASS-21 and QEWP-5), and a short clinical interview by phone and/or information requested by email in those cases where there are doubts about any of the aspects collected through the online instruments.

All candidates who meet the criteria will attend an information meeting about the project in which they will receive written and oral information, and will be asked for their informed consent. Then, participants will be randomly assigned to groups before the pre-treatment assessment sessions. The three groups of the study (intervention, active control and control) will complete all of the evaluations, as well as the follow-ups (see below and Figure 1). Further, all groups will receive the pre-treatment interventions (Motivational Interviewing, nutrition and physical activity sessions). What will differentiate the groups will be, therefore, the treatment: neurocognitive intervention vs. sham vs. usual treatment. The control groups will be offered the treatment sessions (without the assessment components) after the end of the 6-month follow-up.

Sessions will be developed in groups of 5-6 persons. If a participant misses a session he/she can attend another one within 3-4 days. There will be 10 experimental groups of active training = 50 participants; 10 active control groups of sham training = 50 participants; and 10 control groups = 50 participants. The program will comprise 8 weeks including three assessments (pre, intermediate and post-treatment), four intervention sessions, as well as pre-treatment and post-treatment intervention sessions. Also, two follow-up sessions at 3 and 6 months after treatment (see below). Sessions will last about 1 hour and a half.

Sessions will consist of the following (see Figure 1):

1. Informative session (session 1; week 0): All participants will be informed about the aims and the procedure of the research, and they will provide written informed consent.

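### The bias safeguards do not cover the participant, who probably supplies the primary weight readings unchecked and, under usual treatment, can infer the arm, so the BMI contrast with that arm is open to differential reporting.

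*Combined protocol and SAP*

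**What the plan says.** All references are to the combined protocol and SAP.

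- **Section 2.2, Randomization and blinding.** The psychologists who assess are blinded. The plan adds that "since all assessments will be computerized and online, they are not subject to the biases of the evaluator", and that "all participants will be blind to their condition". Only the therapist is unblinded.
- **Section 2.2, sample size.** The trial is sized on "detecting a clinically significant difference in BMI that is the primary outcome measure".
- **Section 2.4 (1).** Weight and height "will be obtained with a pharmacy digital scale". For the week before the pre-treatment assessment, "it will be recorded daily to obtain the baseline weight and then averaged". After that BMI is registered weekly to post-treatment and again at 3 and 6 months.
- **Section 2.4 (2.3).** For the waist measure, "participants should put the tape measure around the waist, just above the navel". Hip circumference is taken the same way.
- **Section 3.** "All assessments and intervention sessions will be delivered online". Everyone hears the aims and procedure before allocation. The control groups are offered the treatment sessions once the 6-month follow-up is over.
- **Section 2.3.** Training sessions, daily practice and reminders go to the experimental and sham arms only.

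**The concern.** The safeguards in Section 2.2 deal with the assessor, the analyst and the participant's knowledge of the arm. They leave two gaps.

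First, a weight read on a scale outside the study is not a computerised assessment, even if it is typed into an online form. If the participant supplies it, a blinded psychologist at the other end protects nothing.

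Second, the blinding of participants cannot be relied on in the usual-treatment arm, because having no sessions is visible to those who have none.

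Together these leave the primary outcome unverified in a contrast that is not blinded in practice. A participant who knows that no training was given, or one who knows that it was, may round, shade or reuse a reading differently. Any average difference between arms in such behaviour adds directly to the estimated effect. BMI also feeds the cost-effectiveness ratio under Objective 4.

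**Working it through.** No figure in the plan is in dispute, so the main check sets the sections side by side. The arithmetic only shows the scale of the risk.

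**Step 1: who supplies the value?** Section 2.4 names the device, and Section 3 puts every assessment online. No study assessor is at the scale, so the likeliest route is that the participant passes on the reading. The text does not state who reads it, who sends it or in what form. For waist and hip no inference is needed, since Section 2.4 (2.3) has participants tape themselves.

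**Step 2: is there a check?** None is described: no ticket, photo, video weighing or witness. By contrast, Section 2.3 has the researcher ask participants to show their phone screens in the app sessions and logs app practice automatically. Remote checking is therefore within the trial's means.

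**Step 3: can participants know their arm?** They are told the aims and procedure. Usual-treatment participants then have no training sessions, practice or reminders, so they can infer their arm. The later offer of sessions points the same way, although the plan does not say when controls learn of it. Experimental and sham participants both have sessions, so that pair is better protected.

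**Step 4: which analyses are exposed?** Section 1 states the hypothesis against sham and against usual treatment. The Section 4 analysis for Objective 1 compares BMI over four moments in a model that includes all three groups. Both the contrast with usual treatment and the overall test are exposed.

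**Step 5: illustration of size.** From the plan: 50 per arm; 35 per arm after the tolerated 30% loss (50 × 0.70); alpha 0.05; planned d = 0.46. Assumed, because the plan gives none of them: an average misreport of 0.5 to 1 kg in one arm and none in the other, height 1.68 m, SD of BMI change 1.0 to 1.5 kg/m², no true effect, and a two-sided test.

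- Bias in BMI = kg / height²: 0.5 / 1.68² = 0.177 and 1 / 1.68² = 0.354 kg/m².
- SE = SD × √(2/n). At n = 50: 0.20 to 0.30. At n = 35: 0.239 to 0.359.
- Standardised bias b = bias / SE. At n = 50: 0.177/0.30 = 0.59 to 0.354/0.20 = 1.77. At n = 35: 0.177/0.359 = 0.49 to 0.354/0.239 = 1.48.
- Rejection rate = P(|Z + b| > critical value).

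| Per arm | Test | Nominal | With bias |
|---|---|---|---|
| 50 | uncorrected (1.96) | 5% | about 9 to 42% |
| 35 | uncorrected (1.96) | 5% | about 8 to 32% |
| 50 | Bonferroni, three pairs (2.394) | 1.7% | about 4 to 27% |
| 35 | Bonferroni, three pairs (2.394) | 1.7% | about 3 to 18% |

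In SD units of change the shift is 0.177/1.5 = 0.12 to 0.354/1.0 = 0.35. That is 26 to 77% of 0.46, if the planned d is read on the same SD. If it is read on a cross-sectional BMI SD of 3 to 4 kg/m² (also assumed), the shift is 0.177/4 = 0.04 to 0.354/3 = 0.12, or about 10 to 26% of 0.46.

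**The case against.** The strongest case against has five parts.

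- **The quoted sentence may be true.** It speaks of the evaluator, and the assessors are blinded. A reader might infer that the plan makes a false statement. The documents do not support that; the fault is that the safeguard stops short of the participant. This part stands.
- **Participant-supplied weight is an inference.** A reader might take it as stated fact that participants report their own weight unchecked. The plan says neither that they report it nor that checks are excluded, and the procedure figure was not available. This stands as a limit on wording. It does not remove the gap, because a plan that leaves the source of its primary outcome unstated needs the same repair.
- **Bias needs a difference between arms.** All arms have motivational interviewing, a diet, an exercise plan and a messaging group, so the pressure to report weight loss is largely shared, and a remembered reading has no obvious reason to favour one arm. This reduces the likely size but does not exclude a difference, because only one arm lacks sessions.
- **The percentages are assumed throughout.** They rest on one-arm shading and, in the first two rows of the table, on an uncorrected test, whereas Section 4 says corrections will always be considered. This stands, and it is why the corrected rows are shown.
- **Some protection already exists.** The pharmacy scale standardises the device, and weekly weights allow a partial plausibility check. Neither verifies a reported value.

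**Conclusion.** The concern holds as a risk to one contrast and to the overall test. It is not a demonstrated bias. Followed as written, the plan describes no verification of its primary outcome and claims participant blinding that is not credible for the usual-treatment arm. Experimental versus sham is better protected, so a reader should not conclude that the whole primary result is compromised.

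Size and direction cannot be derived from the documents. The 9 to 42% range describes what the stated assumptions would do; it is not an estimate of what will happen. It shows that a one-arm misreport averaging 1 kg or less could matter. The change should be made. Confidence is medium, because the route by which weight reaches the database is inferred.

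**What to change.** 1. State in Section 2.4 who reads the weight and height and how the values reach the database.
2. Require a dated scale ticket or photo for each baseline-week reading that enters the average, and at post-treatment, 3 months and 6 months. Staff blinded to arm enter the values. A photo at the pre-treatment session alone would not verify a week-long average.
3. Keep the intention-to-treat analysis of all readings as primary. Add a sensitivity analysis on verified readings, and note that verification is a selection made after randomisation that may differ by arm.
4. Reword Section 2.2 to say that BMI and body measures are obtained by participants (if step 1 confirms this for weight), and limit the participant-blinding statement to the experimental and sham arms.

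Cost: a few protocol sentences, an upload step and a slight burden on participants, heaviest in the baseline week. Interventions, sample size and visits are unchanged. A photo cannot prove who was weighed, so this reduces the risk without removing it.

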1. STARTING HYPOTHESES AND GENERAL OBJECTIVE

HYPOTHESIS: The treatment of excess weight with a comprehensive program based on experimental knowledge about the functioning and modification of the impulsive and executive systems will be effective for the treatment of overweight and obesity. Thus, the neurocognitive training will reduce body mass index (BMI) in people with overweight and obesity, compared to a sham treatment and to only usual treatment. In addition, the neurocognitive program will improve other anthropometric measures (waist circumference, waist-to-hip and waist-to-height ratios), lifestyle behaviors (eating behavior and physical activity), as well as cognitive processes (approach-avoidance bias, food inhibition, food liking and delay of gratification). Finally, the program will show its efficiency in the economic balance of cost-effectiveness and cost-utility.

GENERAL OBJECTIVE: To determine the effectiveness of a comprehensive neurocognitive program for the treatment of excess weight.

1.1. Specific Aims:

Objective 1: To examine the effectiveness of a comprehensive neurocognitive training to reduce BMI in the short, medium and long term (post-treatment, 3-month follow-up and 6-month follow-up).

Objective 2: To study the effectiveness of the comprehensive neurocognitive program to change food behaviors, physical activity and body measures.

Objective 3: To investigate which active ingredients have an impact on the results of the program as outlined below:

3.1. To study the effectiveness of the impulsive training (approach-avoidance bias modification and improvement of inhibitory control) to reduce the approach bias to appetitive foods, increase the inhibitory control, improve the food decision making and modify the valuation of healthy and unhealthy foods.

3.2. To study the effectiveness of reflexive training (implementation of intentions and episodic future thinking) to improve behaviors related to implementation of intentions in healthy eating and physical activity, and to increase delay of gratification.

3.3. To compare the effectiveness of the neurocognitive training (impulsive and reflexive) to reduce BMI and body measures, and to improve food behaviors and physical activity.

3.4. To study the variables related to cognition, affect, stress and non-homeostatic food intake, motivation and personality to predict or mediate the intervention results.

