Before the neurocognitive training, all participants will participate in a Motivational Interviewing group session to maximize motivation and adherence to the program. In the session, participants will be guided through open questions and empathic reflections and affirmations to promote change talk. Participants will share their personal aims to reduce weight, improve their diet and increase their level of physical activity. Further, participants will talk about obstacles they have had on previous occasions, their expectations, and their motivations in regards to weight loss. When needed, information about obesity and nutrition will be provided with the elicit-provide-elicit format. Sessions will end with an individual empathic summary for each participant's interventions.

Importantly, all participants will receive an individualized diet (by a Ph.D. nutritionist) and a physical exercise planning (by a Master's degree physical exercise professional) for the following 6 weeks.

Furthermore, with the aim of equating their knowledge before starting the program, all participants will be provided with 20-minute videos on basic ideas and frequent myths about nutrition and physical exercise. Also, brochures made by the research team about basic nutrition and physical exercise will be provided. Further, participants will have the opportunity if they wish so to attend a group session with a nutritionist and another group session with a physical exercise instructor to ask questions about their individualized diet and physical exercise recommendations and solve any doubt they could have about healthy habits, and thus match and complete relevant information on nutrition and excess weight. These two meetings will be recorded and made available for all participants.

A Whatsapp group will be created for each group of participants to promote their social interactions.

Neurocognitive interventions (experimental and active control groups).

Duration: 4 weeks

Note: The order of phases 1 & 2 will be counterbalanced. One task will be trained in each session, and participants will practice the tasks daily at home for one week (until the next session). Daily training will last approximately 5 minutes. Participants will receive daily reminders to practice via instant messaging on their mobile phones. A weekly pre-post assessment will be conducted for each trained task.

Phase 1: Impulsive training will consist of 2 weekly group sessions of about 60-90 minutes.

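### Participant blinding is claimed for everyone, but the design can support it only between the experimental and sham arms, so the experimental versus usual-treatment contrast is participant-unblinded

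*Combined protocol and SAP*

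**What the plan says.** Section 2.2, under Randomization and blinding, says "Further, all participants will be blind to their condition". No arm is excepted. The same paragraph says that the assessing psychologists and the analysts are blinded and that the therapist alone is not. It adds that, because assessments are computerised and online, "they are not subject to the biases of the evaluator".

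Section 1 hypothesises a BMI reduction "compared to a sham treatment and to only usual treatment", which makes two contrasts for the experimental arm.

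In section 2.3 the training falls under the heading "Neurocognitive interventions (experimental and active control groups"), and within that block "Participants will receive daily reminders to practice via instant messaging on their mobile phones". Section 3 confirms where the arms differ: "What will differentiate the groups will be, therefore, the treatment: neurocognitive intervention vs. sham vs. usual treatment".

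**The concern.** A participant in the sham arm attends sessions, uses the apps and practises at home much as an experimental participant does, so blinding between those two arms is credible. A usual-treatment participant has no training of any kind to mistake for the real one. The blanket statement therefore does not fit the design described a few pages later.

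What is at stake is interpretation. If participants know whether they are being trained, a difference between experimental and usual treatment can reflect the content of the training, the additional contact, the expectation of benefit, or a different way of answering questionnaires. The plan's reassurance about evaluator bias does not reach this, because for many outcomes the participant produces the data. A reader who took the blinding statement at face value would give both contrasts the same protection.

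**Working it through.** There is no planned figure to reproduce. The check sets the relevant sections side by side.

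1. **What the arms receive.** All three get the motivational interview, the individual diet and exercise plans, the nutrition and exercise sessions, and the evaluations (sections 2.3 and 3). Only experimental and sham get the four training sessions in weeks 3, 4, 6 and 7, the home practice and the reminders to practise. With sessions of about 60 to 90 minutes, the training takes 4 × 60 = 240 to 4 × 90 = 360 minutes of group time. Home practice of about 5 minutes a day for a week after each session adds about 4 × 7 × 5 = 140 minutes. If usual-treatment participants also attend for the weekly task assessments, part of the contact is shared, but the training itself is not.

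2. **What participants can know.** Section 2.2 makes a gyroscope phone for app training an eligibility condition for every candidate. Section 3 has every participant told, before allocation, what the study is for and how it will run. Someone screened for app training who is then given none has good grounds to infer the allocation. Someone who is given training can infer that they are not in usual treatment.

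3. **What would keep the usual-treatment arm blind.** The document describes no placebo activity for this arm, no withholding of the number or nature of the arms, and no check on blinding.

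4. **Which contrasts are affected.** Experimental versus sham can be participant-blind. Experimental versus usual treatment cannot, on the procedures described. That is 1 of the 2 hypothesised contrasts. The arm concerned has 50 of 150 participants: 50/150 = 33%.

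5. **Which outcomes are exposed.** From section 2.4:
   - Self-measured: for waist circumference, participants "put the tape measure around the waist, just above the navel, to measure the waist circumference in centimeters", and hip circumference is taken in the same way.
   - Self-reported: the seven-day diary, the 72-hour food intake, MEDAS, IPAQ and the visual analogue scales.
   - Self-reported and used in the economic analysis: SF-36, which supplies the utilities for the QALYs compared across three arms in section 4.
   - BMI: weight and height come from a pharmacy digital scale, so there is less room for misreporting, but effort and expectancy can still act on it.

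6. **Whether the analysis plan separates the contrasts.** Section 4 specifies repeated-measures ANOVA and pairwise effect sizes. It does not say which contrast supports a claim about the training content.

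**The case against.** The strongest reply is that this is loose wording and not a flaw in the trial. The sham arm already supplies a comparison controlled for attention and expectancy. Assessors and analysts are blinded in every contrast. Usual treatment is a legitimate effectiveness comparator, and Objective 4 needs it. Usual-treatment participants also receive a credible programme, and the consent pages are not available, so what they were told about the arms cannot be verified. All of this stands. It limits the point to the blinding statement and to what each contrast can show, and no analysis is shown to be invalid. It does not rescue a statement that covers all participants.

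Four stronger readings are tempting, and the documents do not support them.

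- **The usual-treatment arm has no sessions or apps.** It has motivational, nutrition, exercise and assessment sessions, including the intermediate assessment in week 5. Because all groups complete all evaluations, and some of these run on the Tilt Task and Food Trainer apps, it may use the apps for assessment. The figure that would settle this is not shown.
- **The contrast is open-label.** That ignores the stated blinding of assessors and analysts.
- **The later offer of training reveals the arm.** The text reads "The control groups will be offered the treatment sessions (without the assessment components) after the end of the 6-month follow-up". It covers both control groups, comes after the last outcome assessment, and is not said to be announced in advance.
- **The bias can be sized against the planning effect of 0.46.** The documents give no amount of misreporting and no SD of BMI change. Section 4 standardises between-group effects by the pooled baseline SD, while the standardiser behind 0.46 is not stated. Any percentage would reflect the assumptions chosen.

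**Conclusion.** The statement in section 2.2 is wrong as written. Participant blinding is supportable between experimental and sham, and not for the usual-treatment arm: 50 of 150 participants and one of the two hypothesised BMI contrasts. The accurate description of that contrast is participant-unblinded, with assessors and analysts blinded.

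This rests on two readings. The first is that the training, practice and reminders are confined to the arms named in the section 2.3 heading, which section 3 supports. The second is that participants who know the study involves app training will notice its absence. That is likely given the eligibility condition and the information meeting, but it is an inference. The direction and size of any bias are not established. The three-arm design is sound; the blinding claim and the interpretation attached to it need correcting.

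**What to change.** - **Section 2.2:** replace the blanket sentence with a statement that participants in the experimental and sham arms are blind to which training they receive, and that usual-treatment participants are not blind.
- **Sections 1 and 4:** state that claims specific to the content of the cognitive training rest on experimental versus sham. Keep experimental versus usual treatment as a participant-unblinded comparison of training plus contact, and describe it that way in the three-arm economic analysis too.
- **Optional:** add one arm-guess question to the debriefing that section 3 already places after the interventions. It would also show whether blinding held between experimental and sham.

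The cost is a few sentences and, if wanted, one debriefing item. No visits, sample size or procedures change. The downside is a more modest claim for the usual-treatment contrast. Demoting that contrast any further would be a preference and is not needed to correct the error.
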